4.1. Enrolment/Inclusion Procedures

The study will be conducted in approximately 8 investigational centres in the DRC and possibly in other countries suitable for the conduct of the study.

Patients may be enrolled in different ways:

- a. Children may be brought to the investigational centre spontaneously by their legal representative (a relative of the child will be considered to be a legal representative) and will undergo routine assessments at the centre, including testing for *T.b. gambiense* in blood, lymph and CSF.
- b. Children may be referred to the investigational centre after being diagnosed with stage-1 or early stage-2 HAT by the mobile teams in the

field (see Section 1.4 Routine Case Detection and Management; p 20). Their legal representative will receive a staging certificate from the mobile team indicating what assessments were performed. If the mobile team did not perform a lumbar puncture, it will be done at the investigational site.

- c. A traumatic lumbar puncture will be considered as uninterpretable by the laboratory technician if red blood cells are visible in the CSF, hindering interpretation of the analysis. In this case, lumbar puncture will not be repeated and the patient's status will be considered as undetermined as concerns disease staging. The undetermined status has no impact on the primary analysis since it is not stratified by disease stage.
- d. Each investigational centre is supplied with a new microscope, equipped with a camera that can capture video (maximum 5 seconds of video) and still images during detection of trypanosomes on the slides analysed, as well as images of cell counts in the samples analysed, i.e. the blood, lymph and CSF. The video and still images will be identified by patient, day and time of collection, and will be rendered anonymous, as with other study data, in order to ensure patient confidentiality. The images will be saved and stored on site, as well as in a specific database (Power Folder).

During the screening process prior to inclusion and before the informed consent form is signed, patients will be considered as "pre-screened patients". Children who fulfil the pre-inclusion criteria, which do not require study-specific procedures, will be invited to participate in the study through their legal representative who will receive all necessary information to obtain informed consent. The children will also be informed of their right to refuse to participate in the study, taking suitable precautions and using age-appropriate language.

For patients who are under the legal age to be enrolled, their legal representative must sign the informed consent form after receiving explanations from the Investigator and before any study-specific procedures are performed. The patients will then be considered as a "screened patients".

As mentioned above, initial study-specific procedures do not include lumbar puncture, which is performed routinely. However, the project team will endeavour to provide the medical teams with the possibility of performing lumbar puncture with the use of an equimolar mixture of oxygen and nitrous oxide (EMONO), the feasibility of which is currently being assessed.

The Investigator or a delegate must record the date of the screening visit, the patient's initials, the patient's number, referral source, status at the time of the screening visit, date of collection of informed consent and date of enrolment/ inclusion, as well as the treatment number or the reason for non-enrolment, if appropriate.

The enrolment/inclusion procedures must be carried out between 1 and 15 days before the planned start of treatment in the study. The procedures are described in Section 6 Schedule of Assessments (p 43). The procedures include a complete history-taking, a physical examination, testing and treatment for malaria, treatment for helminthiasis, haematological and biochemical assessments, ECG and a urine pregnancy test for girls ≥12 years of age.

4.2. Pre-inclusion / Pre-exclusion Criteria

The pre-inclusion/pre-exclusion criteria can be checked before informed consent is obtained since no study-specific procedures are involved.

Pre-inclusion Criteria

- Between 6 and 15 years of age;
- Body weight at least 20 Kg;
- Male or female;
- Able to ingest at least one complete meal per day (or at least one sachet of Plumpy'Nut[®]);
- Able to swallow the 600-mg tablets of fexinidazole;
- Karnofsky score > 50 (see Appendix 2 Karnofsky Performance Scale; p 89);
- Evidence of trypanosomes in blood and/or lymph and/or CSF;
- Having a permanent address and able to comply with the schedule of follow-up visits.

For the purposes of the study, patients will be stratified based on the following criteria:

Patients with stage-1 HAT

- Trypanosomes in blood and/or lymph
- No evidence of trypanosomes in CSF
- CSF WBC $\leq 5/\mu$ L

Patients with early stage-2 HAT

- Trypanosomes in blood and/or lymph
- No evidence of trypanosomes in CSF
- CSF WBC > $5/\mu$ L and $\leq 20/\mu$ L

Patients with late stage-2 HAT

• Trypanosomes in blood and/or lymph

and

CSF WBC > 20/µL

Or

• Trypanosomes in CSF

The strata will be self-weighted.

Pre-exclusion Criteria

- Body weight strictly less than 20 Kg;
- Severe malnutrition, defined as Body Mass Index < 16. (–2 standard deviation);
- Unable to take medication by the oral route;
- Pregnancy or breast-feeding;
- Clinically significant medical condition (other than HAT) that could, in the opinion of the Investigator, jeopardise the patient's safety or interfere with participation in the study, including, but not limited to significant liver or cardiovascular disease, suspected or proven active infection (including HIV infection), CNS trauma or seizure disorder, coma or consciousness disturbances;
- Severely deteriorated general status, including as a result of cardiovascular shock, respiratory distress or end-stage disease;
- Any condition (excluding HAT-specific symptoms) that affects the patient's ability to communicate with the Investigator as required to complete the study;
- Any contraindication to imidazole drugs, i.e. known hypersensitivity to imidazoles;
- Prior treatment for HAT in the previous 2 years;
- Prior enrolment in the study or prior intake of fexinidazole;
- Foreseeable difficulty complying with follow-up, including family of migrant workers, refugee status, itinerant trader, etc.;
- Active alcohol or drug addiction.

4.3. Inclusion and Exclusion Criteria

Once the Investigator has checked that the patient fulfils the pre-inclusion/preexclusion criteria, s/he will invite the patient and legal representative to participate in the study and initiate the process for collecting informed consent (see Section 14.2 Informed Consent Process; p 73). Treatment for concurrent malaria or helminthiasis will be initiated, if necessary, and further investigations will be performed.

The inclusion and exclusion criteria will then be checked, just prior to inclusion.

Inclusion Criteria

- Signed informed consent form from one parent or from the legal representative;
- Assent from the child to participate in the study, collected in the presence of an impartial witness.

Exclusion Criteria

- Refusal to participate in the study, expressed by child;
- Clinically significant laboratory test abnormality, with:
 - alanine aminotransferase and/or aspartate aminotransferase more than 2 times the upper limit of normal (ULN),
 - total bilirubin more than 1.5 x ULN,
 - severe leukopenia at < 2000/mm³,
 - potassium < 3.5 mmol/L,
 - any other clinically significant laboratory test abnormality (see Investigator manual for details);
- Pregnancy confirmed by a positive urine pregnancy test within 24 hours prior to the start of treatment (see Section 5.8.3 Contraception; p 41) – for girls ≥ 12 years of age.
- ECG abnormality as assessed by central cardiologist.
- QTcF interval ≥ 450 msec on automatic reading, if the first reading is abnormal, a second reading will be performed at least 10 to 20 min after placing the patient in the resting position.
- Not tested for malaria and/or not having received appropriate treatment for malaria (see Section 5.8.1 Malaria; p 40).
- Not having received appropriate treatment for soil-transmitted helminthiasis (see Section 5.8.2 Helminthiasis; p 40)

The following criteria are considered to be temporary exclusion criteria

- Recovery period after treatment for malaria and/or treatment for helminthiasis, i.e. approximately 3 days.
- Abnormalities on laboratory tests or ECG that can be controlled within a few days after the initial assessment. If the value returns to normal or is not considered clinically significant, the patient can be included in the study.

Patients who fulfil the inclusion and exclusion criteria will be referred to as "included patients".

Patients who are excluded will be treated in accordance with usual practice in the centre, and the reasons, as well as the date, for exclusion from the study will be recorded.

5. Treatments

5.1. Investigational Product

Given the overall dosing regimen and formulation available, i.e. 600-mg tablet, the dosing regimen will be adapted to the child's body weight, as follows:

- Body weight \geq 20 kg and < 35 kg:
 - o 1200 mg from Day 1 to Day 4
 - o 600 mg from Day 5 to Day 10
- Body weight \geq 35 kg (same regimen as for adults)
 - o 1800 mg from Day 1 to Day 4
 - 1200 mg from Day 5 to Day 10

Fexinidazole as 600-mg tablets, will be administered by the oral route, after a meal, i.e. within 30 minutes after starting the meal.

Fexinidazole will be provided by DND*i*, [name].

5.2. Reference Treatment

Not applicable.

5.3. Treatment Allocation

All patients will receive the same treatment.

The number of the treatment pack will be recorded in the patient's file and on the pharmacy log sheet.

Patient participation in the study will be considered to be finished when the last protocol-planned visit has been performed, i.e. the last visit at M18.

5.4. Labelling and Packaging of Investigational Product

Fexinidazole tablets will be packaged in aluminium-aluminium blister packs. Each blister pack will contain the number of tablets necessary for one day of treatment, i.e. 3 tablets for the first 4 days, and 2 tablets for the next 6 days. The 10 blister packs will be packaged in an individual treatment pack for each patient.

For patients who receive only 2 tablets, i.e. 2 x 600 mg, from Day 1 to Day 4 and 1 tablet, i.e. 1 x 600 mg, from Day 5 to Day 10, the Investigator will administer only the required number of tablets and will leave the unused tablet in the blister-pack. Study monitors will check the number of unused tablets at each monitoring visit.

The labelling of the secondary packaging will display the following information:

- Name of Sponsor*, name and contact details for the Coordinating Investigator or Principal Investigator
- Study number*
- Drug name* and dosage strength*
- Dosage form*, route of administration*, number of dosage units*
- Instructions for use
- Statements "For clinical study use only"* and "Keep out of reach of children"
- Batch number* and treatment pack number*
- Expiry date and storage conditions

The information items marked with an asterisk (*) will also be displayed on the primary packaging of the IP.

Information on fexinidazole will be provided in the Investigator Brochure attached to the protocol submitted to the National Authorities.

5.5. Accountability of Investigational Product

The IP will be shipped to the study coordination site (DND*i* Kinshasa), or directly to the investigational sites, depending on the logistical constraints at each site.

Study-specific forms will be used for accountability of the IP. Appropriate records concerning receipt, use, returns, loss and any other disposition of the IP will be maintained by the Investigators on site, or their delegates, under the supervision of the Principal Investigator. Study monitors will check accountability of the IP during on-site monitoring visits.

All IP must be stored in a locked room, or a locked cabinet if no specific room is available, at each investigational site, with access restricted to the nurse in charge of the pharmacy or to authorised study personnel.

The supplies of fexinidazole for the study must not be used for purposes other than the present protocol. The Investigator and the site staff may not, under any circumstances, provide other Investigators or healthcare services with the IP, or allow the IP to be used other than as described in this protocol without prior written approval from DND*i*.

5.6. Storage of Investigational Product

The IP does not require refrigerated conditions during shipping or storage.

Fexinidazole should be stored at a temperature not exceeding 30°C. Long-term stability studies have shown that fexinidazole, stored in the bottle, remains stable at 30°C under conditions of high humidity.

Fexinidazole must be protected from light. This condition is ensured by the fact that the IP is packaged in aluminium-aluminium blister packs.

The stability of the tablets in the aluminium-aluminium blister packs will also be monitored in the context of regulatory stability studies.

The storage conditions, including the temperature, must be monitored by the study personnel and appropriate records should be available.

5.7. Anonymity

This is an open-label study. All persons involved in the study will know what treatment is been administered. The patient's identity will be coded, but not for the team of care-givers and the study monitors.

5.8. Concomitant Treatment

5.8.1. Malaria

All patients will undergo a test to detect malaria. All patients with a positive thick smear and/or rapid diagnostic test (RDT) should receive treatment.

Prior to starting treatment for HAT, malaria will be treated with Coartem®, unless there are individual contraindications, such as hypersensitivity to one of the components, or severe malaria. All existing artemisinin-based combination therapies against malaria have effects on the QT interval. Coartem® was chosen because its effects on QT-interval prolongation are well known, moderate and well quantified (19). The choice was also made in order to minimise confounding factors regarding the assessment of fexinidazole-related QT-interval prolongation. The Sponsor will provide Coartem® free of charge.

In patients with a contraindication to Coartem®, the Investigator can choose another antimalarial agent. The choice must be documented.

Treatment for malaria will be followed by a recovery period of at least 3 days between the last dose of the antimalarial agent and the first administration of treatment for HAT, as per usual practice in the investigational centres.

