5.8.2. Helminthiasis

Treatment for helminthiasis, with mebendazole or albendazole, will be provided free of charge by the Sponsor for use as per usual practice in the investigational centres.

Treatment for helminthiasis will be followed by a recovery period of at least 3 days between the last dose of the antimalarial agent and the first administration of treatment for HAT, as per usual practice in the investigational centres.

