6.1. Timing of Assessments

The timing of assessments is summarised in Table 3 (p 95).

- D-15 to D-1: Patient screening with detection of *T.b. gambiense*, pre-treatment of concomitant helminthiasis and/or malaria, if any, and ECG.
- D-4 to D-1: Baseline assessment, laboratory screening.
- D1 to D10: treatment period.
- D10 to D12: sampling for PK analyses.
- D11: EOT visit.
- D13 to D18: EOH visit; if the end of hospitalisation is extended beyond D18, the EOH visit should be performed on D18 and an additional unscheduled visit should be performed at hospital discharge.
- Additional follow-up visit: at 9 weeks after D1, i.e. D64 to D70, for patients who reach this visit starting in mid-December 2014.
- Follow-up visits: at M3, M6, M12 and M18 see Table 2 Theoretical Schedule of Visits and Acceptable Leeway). The timing of these follow-up visits is calculated from D11 (EOT).

Theoretical schedule of visits	Ideal timing of visits	Acceptable leeway*	
EOT visit	D11 after the Start of Treatment (SOT)	Between D11 and D12 after SOT	
	(D1 after EOT)	(D1 or D2 after EOT)	
EOH visit	Between D13 and D18 after SOT (D3 and D8 after EOT)	D18 at the latest	
Week 9 after D1	D64 to D70		
3 months	3 months ± 1 week after EOT	2-4 months after EOT	
6 months	6 months ± 2 weeks after EOT	5-9 months after EOT	
12 months	12 months ± 4 weeks after EOT	10-16 months after EOT	
18 months	18 months ± 4 weeks after EOT	17-21 months after EOT	

Table 2 - Theoretical Schedule of Visits and Acceptable Leeway

* The acceptable leeway for the visits starts on the first day of the period mentioned and ends on the last day of the period mentioned.

For the purposes of the study, patients will be hospitalised from their arrival at the hospital/investigational centre until D18. They will be permitted to leave hospital from D11 onwards, if their clinical status allows it.

Any additional unscheduled visits that may take place must be recorded in the CRF.

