6.2.3. Baseline Assessment

The following assessments will be performed to assess the patient's baseline status and confirm the patient's eligibility to participate in the study just before the start of treatment.

- Review of inclusion and exclusion criteria;
- Karnofsky Performance Score;
- Vital signs including body temperature, blood pressure and heart rate;
- Verification of clinical signs and symptoms of HAT;
- Physical and neurological examinations;
- Collection of concomitant treatment;
- Urine pregnancy test for girls ≥12 years of age;
- Laboratory safety assessments (see Appendix 3 Laboratory Tests; p 90)
 whenever possible, all laboratory tests will be performed on fasting patients:

- o Haemoglobin,
- Haematology: WBC, platelet count,
- Biochemistry: albumin (ALB), alkaline phosphatase (ALP), alanine aminotransferase (ALAT), aspartate aminotransferase (ASAT), blood urea nitrogen (BUN), chloride (CI-), creatinine (CRE), glucose (GLU), potassium (K+), sodium (Na+), calcium (Ca2+), total bilirubin (TBIL), bicarbonates (tCO₂) and total protein (TP),
- Urine analysis, i.e. WBC, pH, protein, urobilinogen, blood, nitrites, glucose, ketone bodies and bilirubin;
- Digital ECG recording (CarTouch®): triplicate tracings to assess QT interval. The recordings will be transmitted electronically for centralised reading of QT interval.

If the assessments mentioned in Section 6.2.2, i.e. haemoglobin, haematology, biochemistry and urine analysis, were performed within 4 days prior to the first administration, the findings will be considered as baseline values and the tests will not be repeated at the Baseline Assessment.

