9.10. Other Analyses

PK Data

- Fexinidazole, M1 and M2 concentrations in whole blood and CSF, as well as PK parameters derived from a population PK model.
- Analysis of all PK samples will be centralised. A population PK model will be developed using Nonmem software. The model will be fitted on rich sampling data from phase-I studies and used for sparse sampling data from phase-II studies. The model will be used to estimate population PK parameters, including clearance (CL) and volume of distribution (Vd). All of the analyses and statistical methods, including data conventions, will be described in detail in a separate SAP, which will be finalised prior to database lock.
- Correlations between blood and CSF concentrations will be described on samples collected at the EOT visit. Correlations between blood and CSF concentrations, on the one hand, and the success rate/AE rate, on the other hand, will be described.

ECG Data

- QT/QTcF interval (mean, range and categories) at the various timepoints.
- Prolongation of QT/QTcF interval in relation to baseline.

All of the analyses and statistical methods, including data conventions, will be described in detail in a separate SAP, which will be finalised prior to database lock.

10. Steering Committees

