Appendix 4 - Tables

Table 3 – Schedule of Study Procedures

Protocol-planned procedures and forms to be completed	Pre- screening and Screening	Baseline	Treatment period						l	Follow-up period (months)						
Timepoint →	D-15 to D-1	D-4 to D-1	D1	D2	D3	D4	D5	D6	D7	D8	D9	D10	D11 (EOT)	D12	D13-D18 (EOH)	3 - 6 - 12 - 18
Detection of parasite in blood and/or lymph	х												х			x
Lumbar puncture (parasite and white blood cells in CSF)	x												x ² D10H24			x ¹
Informed consent (before any additional medicines or study-specific procedures)	x	Check														
Pretreatment of helminthiasis (+ 3-day recovery period)	x															
Rapid diagnos ic test and/or hick blood smear for malaria	x															
Pretreatment of malaria if necessary (+ 3-day recovery period)	x															
Karnofsky score	х	Check														x
Safety ECG*	X ⁴	Check		х	х	х							х			
Urine pregnancy test ³		X (D-1)													х	x (3 months only)
Inclusion and exclusion criteria	х	х														
Demographic data	х															
Medical history	х															X ⁵
Signs and symptoms of HAT		х													х	x
Vital signs	х	х					х			х			х		х	x
Physical examination		x				İ	х			х			х		x	x
Neurological examination		x				İ	х			х			х		x	x
Haematology/biochemistry*		х				İ	х			х			х			x ⁶
Urine analysis*		х											х			

¹ Except at 3-month visit, unless patient has signs or symptoms of HAT.

² Sampling at EOT to be performed on first 30 patients:

• If no treatment failures are reported in the first 30 patients and if systemic exposure reaches the target concentrations, no sampling will be performed on subsequent patients

• If at least 1 failure is reported in the first 30 patients, sampling will continue in subsequent patients for follow-up on efficacy

³ Only female patients \geq 12 years of age.

⁴ ECG to be sent in electronic format for central reading – await cardiologist's report prior to including the patient in the study.

⁵ Record NEW events since previous visit.

⁶ At 9 weeks after D1, only sampling for haematology and biochemistry, physical examination (including vital signs) and neurological assessment are to be performed.

⁷At 6-month follow-up visit, haematology and biochemistry sampling

* Repeat tests possible, if needed, i.e. if result was abnormal on previous assessment

Protocol-planned procedures and forms to be completed	Pre- screening and Screening	Baseline	Treatment period							EOT Visit until EOH Visit			Follow-up period (months)			

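### The baseline triplicate ECG is not required to follow the antimalarial recovery period, so QTcF change from baseline may be understated in malaria-treated children

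*Protocol*

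**What the plan says.** On the confounder, Protocol section 5.8.1 states: "All existing artemisinin-based combination therapies against malaria have effects on the QT interval". Coartem was preferred because "its effects on QT-interval prolongation are well known, moderate and well quantified", and the same paragraph gives limiting confounding of the fexinidazole QT assessment as a further reason.

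On the washout, the same section says: "Treatment for malaria will be followed by a recovery period of at least 3 days between the last dose of the antimalarial agent". The other end of that interval is the start of HAT treatment. Section 4.3 lists the recovery period after malaria or helminthiasis treatment, about 3 days, as a temporary exclusion criterion.

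On the baseline ECG, section 6.1 gives the window: "D-4 to D-1: Baseline assessment, laboratory screening". Section 6.2.3 places the digital ECG there, with "triplicate tracings to assess QT interval", and Table 3 shows the triplicate ECG in the D-4 to D-1 column. Malaria pre-treatment belongs to the screening window, D-15 to D-1, which overlaps the baseline window.

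On the use of the data, section 6.3.2 schedules the on-treatment triplicates at D4 H4, D4 H23 and D10 (2 to 3 hours after intake). Section 9.10 plans to analyse "Prolongation of QT/QTcF interval in relation to baseline" and leaves the detail to a separate ECG analysis plan.

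On helminthiasis, section 5.8.2 reads: "Treatment for helminthiasis will be followed by a recovery period of at least 3 days between the last dose of the antimalarial agent". Table 3 attaches the interval to the anthelmintic itself: "Pretreatment of helminthiasis (+ 3-day recovery period".

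**The concern.** QTcF prolongation is an expected effect of fexinidazole (sections 1.8 and 1.10), and change from baseline is a planned ECG analysis. The baseline value is subtracted from every on-treatment value. If the antimalarial is still lengthening QT when the baseline triplicate is taken, and that effect has faded by D4 or D10, the subtraction removes too much and fexinidazole looks safer than it is.

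The study has one group, so no control arm would reveal or cancel such a shift. No later analysis can recover a clean baseline that was never recorded. The ECG timing is fixed in the protocol, so the remedy has to be made there.

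**Working it through.** The protocol states no figure on this point that could be reproduced. The check is calendar arithmetic followed by an illustrative sensitivity calculation.

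**Calendar.** Days run D-1, D1 with no Day 0 (assumption). The three-day minimum can be read in two ways.

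| Reading of the minimum | Last antimalarial dose | D-4 | D-3 | D-2 | D-1 | D1 | D4 | D10 |
|---|---|---|---|---|---|---|---|---|
| 3 days' difference | D-3 | -1 | 0 | 1 | 2 | 3 | 6 | 12 |
| 3 clear days | D-4 | 0 | 1 | 2 | 3 | 4 | 7 | 13 |

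Entries are days since the last dose.

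- First reading: D-3 is a dosing day, and so is D-4 if the course spans more than one day (assumption; the protocol does not give its length). D-2 and D-1 fall inside the recovery period.
- Second reading: D-4 is a dosing day, and D-3 to D-1 are the three recovery days.
- Under either reading, no day in the D-4 to D-1 window follows a completed recovery period. Pre-dose on D1 does.

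The whole window is clear only when the last dose is early enough for D-4 to qualify. That means D-7 or earlier on the first reading (7 - 4 = 3 days) and D-8 or earlier on the second (8 - 4 = 4 days). The D-15 start of screening allows this but does not require it.

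**Direction and possible size.** Let e0 be the residual antimalarial QT effect at the baseline ECG, t its half-life in days, and gap the days from baseline to on-treatment ECG. Then

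understatement of change from baseline = e0 × (1 - 2^(-gap/t)).

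The gaps are 6 and 12 days for a D-3 baseline (to D4 and D10), and 4 and 10 days for a D-1 baseline. Both e0 and t are assumptions, because the protocol gives neither.

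| Assumed e0 | Understatement for t = 1 to 6 days |
|---|---|
| 2 ms | 0.7 to 2.0 ms |
| 5 ms | 1.9 to 5.0 ms |
| 10 ms | 3.7 to 10.0 ms |

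Example at the lower end: 2 × (1 - 2^(-4/6)) = 0.7 ms. If the effect barely fades between baseline and D10 (t very long), the understatement is about 0. If treatment ended well before D-4, e0 itself may be negligible.

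The group mean is diluted by the share of children affected, which the protocol also does not give. At e0 = 5 ms and an understatement of 5.0 ms, assumed shares of 10%, 30% and 60% give 0.5, 1.5 and 3.0 ms.

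**The helminthiasis wording.** Section 5.8.2 measures the recovery after anthelmintic treatment from the last antimalarial dose. A child without malaria has no such dose, so the interval is undefined. Section 4.3 and Table 3 both attach a recovery period to the helminthiasis treatment. The passages conflict.

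**The case against.** The strongest reply is that the protocol implies a sequence: treat, recover, then take the baseline. Section 4.3 makes the recovery period a temporary exclusion, section 6.2.3 reviews the eligibility criteria at the Baseline Assessment, and Table 3 puts malaria pre-treatment with its recovery period in the screening column. This has weight: an ECG taken during Coartem dosing runs against the evident intent. But the exclusion delays inclusion and does not time the ECG, the two windows overlap, and no sentence states the sequence. The gap in wording remains.

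Several stronger conclusions that a reader might draw are not supported:

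- *That fexinidazole's QTcF prolongation is underestimated.* This needs treatment ending near the minimum interval, a residual effect at the baseline ECG, and fading by D4 or D10. The protocol establishes none of the three.
- *That a stated fraction of the signal is lost*, taking the 30 ms range in section 1.8 as the denominator. That figure describes a limited number of individual cases, not a mean effect.
- *That the schedule defeats the choice of Coartem.* Using one well-characterised agent still limits confounding, whenever the baseline is taken.
- *That the safety stops are weakened.* The QTcF limits for eligibility (section 4.3) and discontinuation (sections 6.3.2 and 8.2), and the absolute categories in section 9.10, do not use change from baseline.

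It is also fair to say that a table by antimalarial use belongs in the separate ECG analysis plan, so its absence from the protocol is no defect. The slip in section 5.8.2 does not concern QT and adds no weight to the QT point.

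**Conclusion.** The point holds as a gap in timing. The protocol names a QT confounder but does not require the baseline triplicate ECG to follow the recovery period from it. At the minimum interval, no permitted baseline day does. QTcF change from baseline may therefore be understated in malaria-treated children, in the reassuring direction, provided the antimalarial effect is present at baseline and fades by D4 or D10.

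The size cannot be derived from the protocol. The 0.7 to 10 ms range rests wholly on the assumed residual effect and half-life, and zero is possible. The exposure is confined to one secondary ECG analysis in a subset of unknown size; the primary efficacy analysis is unaffected. The change is worth making because it is cheap and the bias, if present, could not be corrected afterwards. The conflict between section 5.8.2 and section 4.3 with Table 3 is a separate wording error.

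**What to change.** In sections 6.1, 6.2.3 and 6.3.2 and in Table 3, state that the baseline triplicate ECG for the QT analysis is recorded after the recovery period as the protocol already defines it, namely pre-dose on D1. D-1 does not meet this at the minimum interval. D1 lies outside the present D-4 to D-1 window, so the window needs an explicit exception for this recording. The single ECG read by the central cardiologist for eligibility stays where it is, and no treatment or recovery rule changes.

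The cost is protocol wording and less scheduling freedom: sites lose the four-day window and have no spare day if the D1 recording fails. No extra ECG is needed. A pre-dose D1 baseline reduces the problem but cannot guarantee that no antimalarial effect remains, so the ECG analysis plan can also show QTcF change by antimalarial pre-treatment. Table 3 already collects concomitant medication from screening, which makes this feasible.

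Separately, reconcile section 5.8.2 with section 4.3 and Table 3 on which drug's last dose starts the recovery period after helminthiasis treatment.
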